# 6.1.7. Electrocardiogram

At screening, a standard 12-lead electrocardiogram (ECG) will be obtained and interpreted by the Investigator to confirm eligibility. If the screening ECG has been completed within 3 months of scheduled dosing it would not need to be repeated

At screening, ECGs will be conducted after approximately 10 minutes of rest and obtained as outlined in Table 1 and Table 2.

# **6.1.8.** Brain Magnetic Resonance Imaging

As outlined in Table 1 and Table 2, screening and post-dose brain MRIs will be performed. Scans will be performed by trained and certified MRI technicians. The MRI will include the acquisition of scans at each time point with and without IV administered gadolinium contrast enhancement.

The following time windows apply:

- "Screening/baseline" MRI should be performed on or after the Screening Visit, but ≥ 10 days before the D1 visit.
- The MRI obtained for the Part A D15 Visit and Part B D22 Visit should be performed up to 3 days before or on the scheduled visit day.
- MRI at Part B visit D90 should be performed within 2 weeks of the scheduled visit.

MRIs will be performed for assessment of safety only and will be reviewed locally.

Study ANK-700-01 in Relapsing-Remitting Multiple Sclerosis

If a relapse occurs at the time of a scheduled MRI, the MRI should be obtained before initiation of corticosteroid therapy or the MRI should be postponed by 1 month.

If the screening MRI has been completed within 3 months of scheduled dosing it would not need to be repeated as long as the screen fail is not due to MS relapse. If the patient needs to re-screen due to experiencing an MS relapse during the screening period, the patient must wait at least 28 days from the relapse resolution and then a new screening MRI should be obtained (and the rescreening MRI must be at least 28 days from last MRI assessment).

All patients with new neurological symptoms suggestive of MS relapse should have an MRI performed (which may include the spinal column) during an unscheduled visit, if clinically necessary, but before the initiation of steroids (see Section 11.1.2).

Additional details on MRI acquisition procedures are described the imaging acquisition guidelines.

# **6.1.9.** Clinical Laboratory Tests

The following laboratory parameters will be measured at screening and at the time points specified in the Schedule of Assessments (Table 1 and Table 2) and will be analyzed locally by a certified laboratory:

- A serum pregnancy test during screening for all women of childbearing potential (WCBP)
- Serum or urine pregnancy testing for all WCBP before each dose
- Hematology laboratory parameters include white blood cell (WBC) count, hemoglobin, hematocrit, platelet count, and WBC differential
- Blood chemistry laboratory parameters, including blood urea nitrogen, creatinine, glucose, AST, ALT, ALP, bilirubin (total and direct), electrolytes (sodium, chloride, bicarbonate, potassium), amylase, lipase, albumin, magnesium, calcium, and phosphorus
- Coagulation laboratory parameters, including prothrombin time, partial thromboplastin time or activated partial thromboplastin time, and international normalized ratio
- Complete urinalysis with qualitative analysis for protein (dipstick)
- HIV, HBV (hepatitis B surface antigen, hepatitis B core antibody, and hepatitis B surface antibody), and HCV testing (screening only)

Unscheduled assessments should be performed as clinically indicated.

For any out-of-range laboratory findings during screening, repeat laboratory testing may be performed at the discretion of the Investigator. Abnormal laboratory findings at screening should be recorded as medical history only if considered CS.

Clinical laboratory assessments should be performed before ANK-700/PBO infusion when applicable.

Study ANK-700-01 in Relapsing-Remitting Multiple Sclerosis

Laboratory findings assessed by the Investigator as CS, including but not limited to, those findings resulting in a drug interruption/hold/reduction/discontinuation or medical intervention, should be repeated to verify the out-of-range findings, followed to a satisfactory clinical resolution, and reported as an AE(s) (see Section 11.1.1 for definition of an AE).

### 6.1.10. ANK-700 Administration

Detailed instructions on the administration of ANK-700 can be found in Section 10.

### 6.1.11. Pharmacokinetic Sampling

PK sample collection time points are shown in Table 1 and Table 2.

The exact date and time of each sample collection must be recorded for all collected samples.

Refer to the ANK-700-01 Laboratory Manual for details on processing, storage, and shipment of PK samples.

# 6.1.12. Antidrug Antibody Sampling

Blood sample collection time points are shown in Table 1 and Table 2.

The exact date and time of each sample collection must be recorded for all collected samples.

Refer to the ANK-700-01 Laboratory Manual for details on processing, storage, and shipment of ADA samples.

### 6.1.15. Adverse Events

All AEs should be captured on the source documentation and eCRF from the time of signing of ICF through the final Follow-Up Visit/phone call. AEs leading to treatment discontinuation and those considered at least possibly related to ANK-700 should be followed until resolution, return to baseline, or deemed chronic or stable.

All serious adverse events (SAEs) will be immediately reported to the Sponsor from the time of signing the ICF through the Follow-Up Visit/phone call or until the patient has been deemed to be a screen failure. After completion of the AE reporting period (i.e., through the final Follow-Up Visit/phone call), only SAEs attributed to ANK-700 must be reported to the Sponsor.

See Section 11.2 for a full description of the collection and reporting of AEs during this study.

# **6.2.** SAFETY FOLLOW-UP VISIT

All patients in Part A will have a final Follow-Up Visit at D182 ( $\pm 7$  days), 6 months after the single administration of ANK-700.

All patients in Part B will have a final Follow-Up Visit at D365 ( $\pm 14$  days), approximately 1 year after the first administration of ANK-700.

Ongoing AEs considered at least possibly related to ANK-700 treatment should be followed until resolution, return to baseline, or are considered stable or chronic.

### 7. CONCOMITANT MEDICATIONS

### 7.1. PROHIBITED CONCOMITANT THERAPIES

During the first 3 months of the study period, any DMTs not listed as a permitted concomitant therapy to treat RRMS (Section 7.2) or other investigational agents are prohibited, including biologic or nonbiologic therapies. All vaccines are prohibited within 4 weeks before dosing and for 2 months after dosing. Patients should avoid taking biotin-containing dietary supplements throughout the duration of the study.

Patients previously treated with any of the following DMTs must adhere to the washout periods outlined below:

- 3-month washout
  - glatiramer acetate, parenteral steroids, or adrenocorticotropic hormone,
     β-interferon, plasma exchange
- 6-month washout
  - fingolimod, ozanimod, or siponimod
- 12-month washout
  - cytotoxic agents (including but not limited to cladribine, mitoxantrone, cyclophosphamide, azathioprine, and methotrexate), laquinimod, teriflunomide, or IV gamma globulin
- 24-month washout
  - mAb therapy (including natalizumab, daclizumab, rituximab, and ocrelizumab)

After patients have completed the 3-month visit (D90), they may receive alternative DMTs for their MS if judged clinically appropriate by their treating physician or the Investigator.

# 7.2. PERMITTED CONCOMITANT THERAPIES

Patients currently on a stable dose of fumarate (dimethyl fumarate or diroximel fumarate) for  $\geq 6$  months will be allowed to remain on fumarate throughout the study. The dose should remain stable during the screening period and for the first 3 months of the study unless medically necessary to alter.

Any medication considered necessary for the patient's welfare, including non-DMTs used to treat symptoms of MS (e.g., antispasmodics or antidepressants), that is not expected to interfere with the clinical evaluation of ANK-700 may be given at the discretion of the Investigator. In cases involving concomitant therapies whose predicted interference with ANK-700 is unknown to the Investigator, the Sponsor should be contacted for discussion.

Any medication (including over the counter or prescription medications, vitamins, and/or herbal supplements) that the patient receives after enrollment through the last study visit must be recorded on the eCRF.

Anokion US, Inc.

### 7.3. TREATMENT FOR SYMPTOMS OF MS

Patients who experience a relapse during the treatment period may receive treatment with IV methylprednisolone or oral corticosteroids, if judged to be clinically appropriate by the Investigator. If a relapse occurs at the time of a scheduled MRI, the MRI should be obtained before initiation of corticosteroid therapy or should be postponed by 1 month.

See Section 11.1.2 for the protocol-defined criteria for an MS relapse.

### 8. CONTRACEPTION AND PREGNANCY

The effects of ANK-700 on conception, pregnancy, and lactation are unknown.

At screening, all patients who are not surgically sterile or postmenopausal must agree to use a medically acceptable methods of birth control as confirmed by study Investigator (e.g., use of an intrauterine device, a barrier method with spermicide, condoms, any form of hormonal contraceptives, or partner sterility) for the first 3 months of the study (through D90). Hormonal forms of birth control must have been in continuous use for  $\geq 3$  months prior to screening to ensure their effectiveness. Complete sexual abstinence is only acceptable when it is the usual/preferred lifestyle of the patient and has been so for  $\geq 3$  months before screening. Periodic abstinence, calendar timing methods of contraception, or withdrawal are NOT acceptable methods of contraception.

A serum pregnancy test will be administered during screening for all WCBP. A serum or urine pregnancy test will be administered to all WCBP before each dose of study drug and must be confirmed negative before administration of study drug.

### 9. OTHER RESTRICTIONS RELATED TO COVID-19

Patients will be advised to adhere to local requirements for reduction of the public severe acute respiratory syndrome coronavirus 2 (SARS-CoV-2) exposure while ambulatory. All patients should be called 1 day prior to every visit for assessing COVID-19 signs and symptoms and asked not to attend the site if infection is suspected. In addition, patients will be asked whether they have had any contact with a person who has a confirmed infection. If applicable, patients will be referred to the local health care system. Physical distancing and person-to-person contact restrictions should be applied and explained to patients while staying at the study site, if required by local requirements. Where physical distancing is not possible, study participants will be asked to use face masks and/or gloves, if deemed appropriate by the Investigator and site staff and guided by local requirements.

### 10. ANK-700 MATERIALS AND MANAGEMENT

### 10.1. ANK-700 AND PLACEBO

apart, of either ANK-700 or PBO.

dministration of ANK-700 will be by
IV infusion over approximately 30 minutes. For Part A, patients will receive a single IV infusion of ANK-700. For Part B, patients will receive a total of 3 IV infusions, administered 3 days

Additional information is provided in the ANK-700-01 Pharmacy Manual.

### 10.2. DOSAGE AND ADMINISTRATION

Administration will be by IV infusion over approximately 30 minutes.

For Part A, patients will receive a single IV infusion of ANK-700 only (no PBO).

For Part B, patients will receive 3 IV infusions, each administered 3 days apart, of a given dose of either ANK-700 or PBO. All doses will be prepared as outlined in the ANK-700-01 Pharmacy Manual by an unblinded pharmacist.

Study treatment (ANK-700 or PBO) should be administered over approximately 30 minutes under the supervision of a physician or other medically qualified study personnel experienced in the use of IV agents and in a facility equipped to manage medical emergencies. The prepared saline bag and infusion line should be weighed before and after administration. These weights should be recorded using any available scale with a precision to at least one tenth of a gram (0.1 grams). Both weight measurements should be conducted using the same scale to reduce variability. In the event of a Grade 3 infusion-related reaction (IRR), the total infusion duration may be increased to 2 hours or 50% of the rate at which the reaction occurred (please see Section 10.5 for more information). In cases where a temporary interruption is required, the total infusion should be completed within 6 hours of saline bag preparation. See Section 10.5 for detailed guidance regarding infusion administration interruptions because of infusion reactions.

Please refer to the ANK-700-01 Pharmacy Manual for detailed administration instructions.

### 10.3. STORAGE

ANK-700 is supplied in vials for single use. ANK-700 is to be stored at -20°C and protected from light in a temperature-monitored, locked freezer. Additional details on storage conditions are available in the ANK-700-01 Pharmacy Manual.

Study ANK-700-01 in Relapsing-Remitting Multiple Sclerosis

# 10.4. Post-Infusion Medications

No specific post-infusion medications are required for ANK-700, but appropriate medications may be administered at the discretion of the Investigator.

Anokion US, Inc.

### 10.5. INFUSION-RELATED REACTIONS

If an IRR occurs during ANK-700 administration, the following treatment recommendations are provided and may be modified per local treatment standards and guidelines as appropriate.

- Grade 1 (mild): Infusion rate modification not indicated. Administer symptomatic treatment (e.g., antihistamines, antipyretics, antiemetics) as needed. Closely monitor patient until resolution. Prophylaxis with diphenhydramine 50 mg (or equivalent) and/or acetaminophen/paracetamol 325 to 1000 mg is recommended ≥ 30 minutes prior to future ANK-700 infusions.
- Grade 2 (moderate): Slow infusion to ≤ 50% of the original infusion rate and treat symptoms with appropriate medical therapy, including but not limited to antihistamines, antipyretics, and analgesics. Increase monitoring of vital signs as medically indicated until patient is deemed stable. Prophylaxis with diphenhydramine 50 mg (or equivalent) and/or acetaminophen/paracetamol 325 to 1000 mg is recommended ≥ 30 minutes prior to future ANK-700 infusions.
- Grade 3 (severe): Stop infusion and institute appropriate symptom-directed therapy, including but not limited to antihistamines, antipyretics, corticosteroids, bronchodilators, and oxygen. Increase monitoring of vital signs as medically indicated until patient is deemed stable. If the reaction has not resolved within 6 hours, the remainder of the infusion will not be administered, and ANK-700 will be permanently discontinued. After the completion or termination of a restarted infusion because of an IRR, all patients must be monitored until resolution of symptoms or for 2 hours in the absence of additional symptoms. Prophylaxis with diphenhydramine 50 mg (or equivalent) and/or acetaminophen/paracetamol 325 to 1000 mg is required ≥ 30 minutes before future ANK-700 infusions. The next infusion should initiate at a rate of 2 hours per dose, or 50% of the rate at which the reaction occurred. If no IRRs are observed within the first 30 minutes, the infusion rate may increase to the 1-hour-per-dose rate as outlined in Section 10.2. Permanently discontinue ANK-700 upon a second occurrence of a Grade 3 or greater infusion reaction.
- Grade 4 (life-threatening): Stop infusion and immediately institute appropriate symptom directed therapy and supportive measures as necessary, including, but not limited to, corticosteroids, bronchodilators, oxygen/respiratory support, and vasopressors.
   Hospitalization and/or intensive care unit admission may be indicated. Permanently discontinue treatment.

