# **4.3. DOSING FREQUENCY**

In Part A, patients will receive a single IV infusion of ANK-700 on D1.

In Part B, patients will receive a total of 3 IV infusions of either ANK-700 or PBO (double-blind). A single IV infusion will be administered on D1, D4, and D7.

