#### **4.6. DOSE-LIMITING TOXICITIES**

Dose-limiting toxicities for Study ANK-700-01 include any Grade 2 AE not resolving within 14 days or any ≥ Grade 3 AE occurring during the dose-escalation safety monitoring period (D1 to D15 in Part A; D1 to D22 in Part B). DLTs do not include those AEs attributable solely to intercurrent illness or other concomitant medications. Any DLT experienced during the dose-escalation safety monitoring period will result in study pause and review by the SMC.

Any  $\geq$  Grade 4 AE will result in notification to the Food and Drug Administration (FDA) in parallel with the SMC; all study dosing and enrollment will be paused pending review by FDA.

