#### 4.7. Dose Escalation Safety Monitoring Period

In Part A, the dose-escalation safety monitoring period is from the beginning of the IV administration of ANK-700 through the D15 clinic visit. Any AEs that meet the criteria defined in Section 4.6 but occur after the dose-escalation safety monitoring period of Part A, may be considered by the SMC in the evaluation for Part B dose selection.

The dose-escalation safety monitoring period in Part B is from the beginning of the first IV administration of ANK-700/PBO through the D22 clinic visit.

The monitoring period is supported by nonclinical animal data, which demonstrate:

- ANK-700 is cleared from circulation in < 7 minutes, ensuring that > 5 half-lives have elapsed during the safety monitoring period
- T-cell tolerance induction can be observed as early as 1 week after drug administration in nonclinical models, ensuring the mechanism of action will be active and robust during the safety monitoring period
- Immunologically active antigen cannot be detected in animals 7 days after GP-peptide administration, ensuring that any processed antigen will be cleared during the safety monitoring period

AEs and any abnormal clinical parameters, including laboratory findings, observed during this period will be used by the SMC to determine whether dose escalation should proceed.

No patient with a DLT will be replaced.

In both parts, patients will be monitored in the clinic for 8 hours after the completion the first IV administration of ANK-700/PBO. In Part B, patients will be monitored in the clinic for 4 hours after completion of their second and third dose.

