#### 4.9. INDIVIDUAL AND COHORT STOPPING RULES

During the dose-escalation safety monitoring period, any DLT will result in a pause in enrollment and a thorough review by the SMC before treating any additional patients. Any ≥ Grade 4 AE will result in notification of the FDA in parallel with the SMC, and study dosing and enrollment will be paused pending review by FDA.

For Part A, if 1 of the first 3 patients experiences a DLT within the safety monitoring period (D1 to D15) in a given cohort, 3 additional patients will be enrolled and evaluated in that cohort before dose escalation can occur if recommended by the SMC and only after consultation with the FDA for any  $\geq$  Grade 4 AE. If 2 or more patients experience a DLT at a given dose level during the dose escalation evaluation period of Part A (D1 to D15), then that dose level will be considered to have exceeded the non-tolerated dose (NTD), and no further escalation will proceed.

If a patient experiences a DLT during the dose-escalation safety monitoring period of Part B, no additional doses will be administered to that patient. If 1 patient experiences a DLT during the dose-escalation safety monitoring period of Part B, the study will be paused to determine if any dose adjustments are needed and/or if the study should dose any additional patients. For any  $\geq$  Grade 4 AE, the study will only continue after consultation with the FDA. If 2 or more patients experience a DLT during the dose-escalation safety monitoring period of Part B (D1 to D22), then that dose level will be considered to have exceeded the NTD, and no further escalation will proceed.

The maximum tolerated dose (MTD) will be defined as the proximal dose level below the dose exceeding the NTD administered during the study. Of note, dose escalation may not identify an NTD or MTD.

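### In Part B, a Grade 3 infusion reaction at D1 or D4 that resolves within 6 hours bars further dosing under Sections 4.6 and 4.9, yet Section 10.5 says how to give the next infusion

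*Protocol*

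**What the plan says.** Protocol Section 4.6 counts as a DLT "any ≥ Grade 3 AE occurring during the dose-escalation safety monitoring period". The 14-day resolution condition in the same sentence applies to Grade 2 events only. There is one exclusion: "DLTs do not include those AEs attributable solely to intercurrent illness or other concomitant medications". SAP Section 6.1.6 repeats both the definition and the exclusion.

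Section 4.7 sets the Part B monitoring period "from the beginning of the first IV administration of ANK-700/PBO through the D22 clinic visit". Section 4.3 gives the Part B schedule: "A single IV infusion will be administered on D1, D4, and D7". For a patient with a DLT, Section 4.9 states: "If a patient experiences a DLT during the dose-escalation safety monitoring period of Part B, no additional doses will be administered to that patient".

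Section 10.5 deals with a Grade 3 infusion reaction differently. The infusion is stopped, and if the reaction has not resolved within 6 hours the drug is permanently discontinued. Otherwise premedication "is required ≥ 30 minutes before future ANK-700 infusions", and "The next infusion should initiate at a rate of 2 hours per dose, or 50% of the rate at which the reaction occurred". Permanent discontinuation is then reserved for a second reaction of Grade 3 or greater. Section 10.2 also allows a longer infusion after a Grade 3 reaction and sends the reader to Section 10.5.

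**The concern.** The two sets of instructions disagree on whether a patient who has just had a severe infusion reaction is dosed again. One is a categorical individual stopping rule. The other describes premedication, rate and a second-occurrence limit for later doses, and mentions neither DLTs nor Section 4.9. Neither document says which prevails.

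This is a first-in-human trial with infusions 3 days apart. A site that follows Section 10.5 as written would re-expose a patient whom the stopping rule excludes from further dosing. A site that follows Section 4.9 would withhold doses that Section 10.5 provides for. Sites could therefore treat the same event differently.

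**Working it through.** The plan states no figure to reproduce on this point. The check traces the rules and then counts the infusions to which the conflict can apply.

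**Is a resolved Grade 3 infusion reaction a DLT in Part B?**
- It is an AE under Section 11.1.1 and meets the Grade 3 threshold in Section 4.6, however quickly it resolves.
- The exclusion covers events due solely to intercurrent illness or other concomitant medications. A reaction to the study infusion is neither.
- D1, D4 and D7 all lie between the first infusion and D22, so every Part B infusion is inside the window.

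It is therefore a DLT, and Section 4.9 stops dosing for that patient.

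**Could the next-infusion text be meant for Part A?** No. Section 4.3 says: "In Part A, patients will receive a single IV infusion of ANK-700 on D1". Part A has no later infusion.

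**Could it mean restarting the interrupted infusion?** No. Section 10.5 covers a restarted infusion in its own sentence and then refers separately to future infusions and to the next one.

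**Further scheduled infusions allowed after a first Grade 3 reaction that resolves within 6 hours:**

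| Reaction at | Remaining infusions | Sections 4.6 and 4.9 | Section 10.5 |
|---|---|---|---|
| D1 | D4, D7 | 0 | up to 2 |
| D4 | D7 | 0 | up to 1 |
| D7 | none | 0 | 0 |

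A reaction unresolved at 6 hours, and any Grade 4 reaction, ends dosing under both sections, so there is no conflict in those cases.

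**Planned infusions at which the conflict can arise.** Section 12.1 plans 24 Part B patients, 16 on ANK-700 and 8 on placebo, with 3 infusions each.
- All Part B: 24 × 3 = 72 infusions, of which 24 × 2 = 48 (D1 and D4) are followed by another.
- ANK-700: 16 × 3 = 48 infusions, of which 16 × 2 = 32 are followed by another.
- Placebo: 8 × 2 = 16 of the 48.

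Sites are blinded in Part B (Section 4.4), so the instructions apply in the same way to both arms. These are counts of opportunities. They say nothing about how often a reaction will occur.

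**The case against.** The best counter-argument is that the two texts differ in force. Section 4.9 is an absolute rule, whereas Section 10.5 calls its content recommendations that local practice may modify. The premedication requirement governs how a future infusion is given and does not order that it be given. A site can withhold the dose and breach nothing in Section 10.5. In addition, any DLT pauses the study for SMC review, so re-exposure would need the site to miss the DLT or overlook Section 4.9 within 3 days. Section 4.10 lists an AE requiring permanent discontinuation among the reasons to stop treatment, and that could be read to include a DLT. The Pharmacy Manual, which is not available here, might settle the matter.

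Some of this stands. The stricter rule can be followed, and the pause lowers the risk. The rest does not remove the conflict:
- Freedom to adapt to local standards is not deference to Section 4.9, and an investigator who applies Section 10.5 unmodified breaks the stopping rule.
- Section 10.5 names the circumstances in which a Grade 3 reaction ends treatment, and a first resolved reaction is not among them. The text presumes re-dosing.
- Section 4.9 describes the pause and review in terms of enrollment, dose adjustments and additional patients. It does not make them the mechanism for deciding the affected patient's next dose.
- Section 4.10 does not name DLTs. Read with Section 10.5, a first resolved reaction does not require permanent discontinuation, so the section settles nothing.
- A Grade 3 event later attributed solely to another medication would escape the DLT rule, but it would not then be an infusion reaction to study drug.
- A site manual should not be the only place where a protocol contradiction on a stopping rule is resolved.

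**Conclusion.** The concern holds. For a Part B patient with a first Grade 3 infusion reaction at D1 or D4 that resolves within 6 hours, Section 4.9 permits no further infusion, while Section 10.5 provides for up to 2 or up to 1 respectively. In this trial the next-infusion text cannot be applied to a scheduled dose without breaching Section 4.9. Part A, D7 reactions, Grade 4 reactions and Grade 3 reactions unresolved at 6 hours are unaffected.

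The conclusion rests on the protocol and SAP alone and assumes that no other study document overrides them. No event rate is given and none is assumed. The defect is an internal inconsistency about patient safety and trial conduct, and the sample size and descriptive methods do not depend on it. It should be corrected even if such reactions prove rare, because the instruction matters only when one occurs.

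**What to change.** Choose one rule and state it in every place.

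**If the stopping rule stands** (the default, since Section 4.9 is categorical): in the Grade 3 bullet of Section 10.5, state that such a reaction in Part B is a DLT, that the patient receives no further scheduled infusion, and that the study pauses for SMC review under Section 4.9. Delete the text on premedication and rate for later infusions from that bullet. Limit the second-occurrence sentence to a restart of the same interrupted infusion, if restart is allowed. Align Section 10.2.

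**If the sponsor and SMC intend re-dosing:** write an explicit exception for Grade 3 infusion reactions resolving within 6 hours into Sections 4.6 and 4.9 and SAP Section 6.1.6.

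A minor point: Section 10.5 cites a 1-hour rate from Section 10.2, which does not state one directly. It follows only as half the 30-minute rate (30 ÷ 0.5 = 60 minutes). If that text is kept, Section 10.2 should give the rate.

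The cost is a wording amendment to the protocol, plus one SAP sentence on the second route. Neither route changes the sample size or the descriptive analyses.

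### In Part B, Section 10.5 provides for further infusions after a Grade 3 infusion reaction that resolves within 6 hours, while Section 4.9 allows none because that reaction is a DLT

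*Protocol*

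**What the plan says.** **DLT definition.** Protocol Section 4.6 counts as a DLT "any ≥ Grade 3 AE occurring during the dose-escalation safety monitoring period (D1 to D15 in Part A; D1 to D22 in Part B"; SAP Section 6.1.6 repeats it. The one exclusion is stated as follows: "DLTs do not include those AEs attributable solely to intercurrent illness or other concomitant medications". The 14-day resolution condition in the same section applies to Grade 2 events only.

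**Stopping rule.** Protocol Section 4.9 says that a Part B patient who has a DLT in the monitoring period receives no more doses. Sections 4.6 and 4.9 also call for a pause and SMC review after a DLT.

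**Reaction management.** Section 10.5 opens by saying that "the following treatment recommendations are provided and may be modified per local treatment standards and guidelines as appropriate". Its Grade 3 bullet tells the site to stop the infusion and treat the patient, and then separates two cases.

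- Unresolved: "If the reaction has not resolved within 6 hours, the remainder of the infusion will not be administered, and ANK-700 will be permanently discontinued".
- Otherwise: prophylaxis "is required ≥ 30 minutes before future ANK-700 infusions". For the dose that follows: "The next infusion should initiate at a rate of 2 hours per dose, or 50% of the rate at which the reaction occurred". If the first 30 minutes pass without a reaction, "the infusion rate may increase to the 1-hour-per-dose rate as outlined in Section 10.2". The last sentence is: "Permanently discontinue ANK-700 upon a second occurrence of a Grade 3 or greater infusion reaction".

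Section 10.2 lets the infusion be lengthened to 2 hours, or slowed to 50% of the rate, after a Grade 3 reaction, and refers to Section 10.5 for detail. None of the text in Sections 10.2 and 10.5 mentions Section 4.6 or 4.9, and Sections 4.6 and 4.9 do not mention infusion reactions.

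**The concern.** A site managing a reaction will turn to Section 10.5. For a Grade 3 reaction that settles quickly, it gives a premedication requirement, a starting rate and a rule for stopping at a second event. All three presuppose another dose. In Part B the same patient has usually just met the DLT definition, and the stopping rule allows no further dose.

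The drug is first-in-human and the next infusion is due three days later. At stake is whether a patient with a DLT could be re-exposed because the operational text says one thing and the stopping rule another.

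**Working it through.** There is no planned figure to reproduce. The check is a comparison of sections followed by a count of doses.

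**Step 1. Is the reaction inside the DLT window?** Section 4.3 puts Part B infusions on D1, D4 and D7. Section 4.7 runs the Part B window from the start of the first infusion through the D22 visit. All three infusions fall inside it.

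**Step 2. Is a resolved Grade 3 reaction a DLT?** Section 4.6 attaches no duration condition to Grade 3 events and makes no exception for infusion reactions. An ordinary reaction to study drug is not attributable solely to intercurrent illness or another medication, so it is a DLT.

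**Step 3. Could Section 10.5 be meant for another setting?** Part A has one infusion, so the next-infusion text has no use there. Nor does the next infusion naturally mean the rest of the same bag. The bullet deals with the remainder and the restarted infusion in separate sentences, then turns to future infusions and a rate per dose.

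**Step 4. Count the doses at issue.** With 3 infusions planned, a reaction on dose k leaves 3 − k. Exposure is that number times the dose level: 0.3 mg/kg in Cohort 4 and 1.0 mg/kg in Cohort 5.

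| Grade 3 reaction in Part B | Further infusions, Section 10.5 read alone | Section 4.9 | Most extra exposure, Cohort 4 | Most extra exposure, Cohort 5 |
|---|---|---|---|---|
| D1, resolved within 6 h | up to 3 − 1 = 2 | 0 | 2 × 0.3 = 0.6 mg/kg | 2 × 1.0 = 2.0 mg/kg |
| D4, resolved within 6 h | 3 − 2 = 1 | 0 | 1 × 0.3 = 0.3 mg/kg | 1 × 1.0 = 1.0 mg/kg |
| D7, resolved within 6 h | 3 − 3 = 0 | 0 | 0 | 0 |
| Any day, unresolved at 6 h | 0 | 0 | 0 | 0 |

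After a D1 reaction, the 2 falls to 1 if a second Grade 3 reaction occurs on D4. Grade 4 reactions end treatment under Section 10.5 as well, so the sections agree there.

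**Step 5. Check the 1-hour reference.** Section 10.2 gives about 30 minutes as the standard duration and 2 hours or 50% of the rate after a Grade 3 reaction. It gives no 1-hour rate, so the step-up sentence points to text that is not there.

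**The case against.** The strongest reply is that other controls stand between the two sections. A DLT pauses the study and brings in the SMC. The schedules give D4 and D7 no visit window, so two further infusions would need the pause to be ignored or lifted within three days. This stands, and it is why the dose figures are ceilings. It does not remove the conflict: the wording on the pause in Section 4.9 concerns enrollment and the treatment of additional patients. The explicit bar for this same patient is the no-more-doses sentence, which Section 10.5 contradicts.

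A second reply is that Section 10.5 offers only recommendations, so Section 4.9 plainly governs. That is the sensible reading, but it is an inference. The documents give no order of precedence, the permitted modification is by local treatment standards, and the Grade 3 bullet itself uses mandatory terms. The sponsor could instead write an exception for infusion reactions into Section 4.6. Letting Section 4.9 control is the conservative choice.

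A third reply is that the redosing text has a legitimate, if narrow, use: a Grade 3 reaction excluded from the DLT definition may be followed by further doses. This stands. The safeguards should therefore be kept for that case.

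**Conclusion.** The contradiction is real and should be fixed. In Part B, a resolved Grade 3 reaction on D1 or D4 that meets the DLT definition leads to no further doses under Section 4.9. Section 10.5, read alone, allows at most 2 or 1, with the exposures tabulated above. The table assumes full planned doses and no effect of the pause.

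A reader might infer more, and the documents do not support it:

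- *That patients with a DLT will be redosed.* The pause and SMC review stand in the way, and the documents give no reaction rate, so no probability can be attached.
- *That the safety tables would be wrong.* The SAP's treatment-discontinuation summary and count of completed infusions would differ according to which section a site followed, but they would report what happened. No analysis defect follows.
- *That the missing 1-hour rate is a separate dosing error of weight.* It matters only where redosing is allowed, and it can be cleared up in the same edit.

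The existence of the conflict is certain from the text. Which section should give way is a judgement, made here in favour of the stopping rule.

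**What to change.** **Section 10.5, Grade 3 bullet.**

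1. Keep the 6-hour sentence and the monitoring sentence for restarted infusions.
2. Then add: *A Grade 3 IRR that meets the DLT definition in Section 4.6 ends dosing for that patient: no subsequent scheduled infusion (D4 or D7) will be given (Section 4.9). If a Grade 3 or greater reaction recurs when the remainder of the interrupted infusion is restarted, stop and do not restart.*
3. Keep the prophylaxis, next-infusion-rate and second-occurrence sentences, introduced by: *For a Grade 3 IRR that does not meet the DLT definition in Section 4.6 only:*
4. Delete the step-up sentence, because Section 10.2 has no 1-hour rate.

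**Section 10.2.** Add that, after a Grade 3 IRR that is a DLT, the 2-hour or 50% rate applies only to the remainder of the interrupted infusion.

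This wording treats the remainder of an interrupted bag as part of the current dose and not as an additional dose under Section 4.9. The protocol does not settle that, so the sponsor should confirm it.

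**Cost.** A wording change in two sections, made by protocol amendment, of which the principal investigator must inform the IRB/IEC (Section 13.4). It adds no procedures, visits or patients, and the SAP does not change.
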